### 8.3 Reporting of Serious Adverse Events by Investigator

All SAEs must be reported by the investigator to the responsible Safety Officer at the KKS Heidelberg within 24 hours after the SAE becomes known using the "Serious Adverse Event" form. The initial report must be as complete as possible including details of the current illness and (serious) adverse event and an assessment of the causal relationship between the event and the trial medication.

The reporting will be performed by sending a completed 'SAE Form' to the KKS Heidelberg.

[contact]**

Only in case of technical faults the SAE Form can be also submitted by e-mail:

**Email: [[contact]](mailto:[contact])**

### 8.4 Reporting of Pregnancies

Female patients taking the IMP prior to knowing about a pregnancy will only be reported if the daily dose at least once was higher than one tablet during the time span of undetected pregnancy. Reporting will be made within 24 hours by using the SAE-form.

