- Existing or intended pregnancy, lactation in patients of the intervention group. If patients in the control group become subsequently pregnant and/or need to breastfeed after randomisation, they will not be excluded from the trial.

All patients who finish the study prematurely will be asked to attend a follow-up visit and to return unused trial medication. The patient must be asked to consent to this last examination. The withdrawal examination will be documented in the CRF.

If a patient does not come to a visit, the patient will be contacted and asked for information. If the patient wants to withdraw and agrees to give explaining reasons, the reason should be documented in the patients file and in the CRF.

In case of early withdrawal, the last aneurysm imaging will be used for the primary outcome analysis (*last observation carried forward*).

If a patient has severe side effects from one component of the intervention only, (e.g. severe orthostatic hypotension from intensive blood pressure control or major gastrointestinal bleeding from ASA), it can be decided to adjust or stop the component of the intervention causing the side effects, while continuing the other component of the intervention.

For documentation of AEs and SAEs see 8.1.6 and 8.2.

| Term                         | Definition   | Comment/ Sample  |
|------------------------------|--|--|
| Drop-out, study              | 
Participation terminated completely, including follow-up
 
Possible reasons:
 
 
• Patient withdraws consent: Withdrawal
 
• Patient moved/cannot be contacted
 
• Interventions cannot be performed due to medical reasons
 
• Non-compliance of patient
 
 
Drop-out after completion of study intervention:
Lost to follow-up
 
Final examination will be performed, if patient agrees. Study-Completion/ Withdrawal-form will be completed.
 | 
ITT-sample
 
ITT-sample (if study intervention completed)
  |
| Drop-out, study intervention | Termination of study intervention, follow-up once as per protocol.   | ITT  |
| Screening-failure            | 
Exclusion criteria given prior to screening / enrolment:
 
Patient will be recorded at screening list, but will not be provided with a patient number.
   | -  |

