#### 5.1.2 Characterisation of study medication

The study medication is:

|  |   |
|--|---|
| International Nonproprietary Name (INN): | Acetylsalicylic acid                              |
| ATC code:                                | B01AC06   |
| Pharmaceutical formulation:              | Tablets   |
| Dose                                     | Daily, 81 – 100 mg (depending on country)         |
| Mode of administration:                  | Oral  |
| Storage instructions:                    | Store below 30°C / 86° F, protected from humidity |

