### 5.4.2 Dosage Schedule

The study medication is given only to patients who have consented to study participation and who are randomized to the intervention group.

Maximum duration of treatment: 120 months  
Maximum dose allowed: 100mg ASA daily, orally

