#### 5.4.5 Adjustments to dosage of the IMP in the individual trial subject

- A) The use of ASA may be interrupted, if a patient needs surgery during the course of the clinical trial. It will be resumed as soon as possible after surgery.
- B) No changes in IMP dosage are intended or permitted, even in case patients require a higher dose of ASA for other indications. However, if patients are medically required to be treated with higher doses of ASA (e.g. due to cardiovascular event) while being on treatment with the IMP, the treating physician can prescribe ASA as required and the IMP will be stopped for the time in which ASA is prescribed.
- C) For safety data, patients of the intervention group, who received concomitant long-term ASA will be analysed as per protocol, patients of the control group as ITT.

No further adjustments are planned.

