### 8.1.2 Serious Adverse Event

A serious adverse event (SAE) is one that at any dose:

- Results in death
- Is life-threatening (the term life-threatening refers to an event in which the subject was at risk of death at the time of event and not to an event which hypothetically might have caused death if it was more severe)
- Requires hospitalisation or prolongation of existing hospitalisation\*
- Results in persistent or significant disability/ incapacity\*\*
- Is a congenital anomaly/ birth defect or
- Is otherwise medically relevant

\* Hospitalisation for performing *preventive* aneurysm treatment is not classified as an SAE. Hospitalisations for disease-related procedures (surgery, imaging, laboratory tests) or any procedures planned before entry into the study are not considered SAEs. Hospitalisations for social reasons in the absence of an adverse event are not classified as SAEs either.

\*\* Persistent or significant disability or incapacity means that there is a substantial disruption of a person's ability to carry out normal life functions. The irreversible injury of an organ function (e.g. paresis, diabetes, cardiac arrhythmia) fulfils this criterion.

Medical and scientific judgement will be exercised in deciding whether expedited reporting is appropriate in other situations - such as important medical events that may not be immediately

life threatening or result in death or hospitalisation but may jeopardise the patient or may require intervention to prevent one of the other outcomes listed above. These should also usually be considered serious (examples of such events are intensive treatment in an emergency room or at home for allergic bronchospasm; blood dyscrasias or convulsions that do not result in hospitalisation; or development of drug dependency or drug abuse).

SAE reporting will be coordinated by the KKS pharmacovigilance.

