## 8.2 Period of Observation and Documentation

Adverse events (AEs) will be ascertained by the investigators using non-leading questions, noted as spontaneously reported by the patients to the medical staff or observed during any measurements on all study days. The observation period begins with the randomisation and ends with the last study visit, 30 days +/-10 days after end of treatment visit (or after withdrawal) (i.e. follow-up-visit). AEs will be documented in the patient file and in the CRF. All subjects who present AEs, whether considered associated with the use of the trial medication or not, will be monitored by the responsible investigator to determine their outcome; this applies to withdrawals too (see also 8.1.7).

The end date of the SAE is defined typically the same as for AEs. The end date of the SAE must not be later than the end date of the corresponding AE.

AEs and SAEs that are on-going at the time of death are considered not resolved or resolving.

The patients should report any AEs occurring during the outpatient part to the study centre by phone.

|   |   |                               |
|---|---|-------------------------------|
| Clinical Trial Code: Protect-U
EudraCT: 2017-000514-35 | Trial Protocol
Version 07 - August 23 - 2022 | Page 44 of 62
CONFIDENTIAL |
|---|---|-------------------------------|

All SAEs and their relevance for the benefit/risk assessment of the study will be evaluated continuously during the study and for the final report. All SAEs will be documented in the "Serious Adverse Event" form (see 8.3).

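### Section 8.4 reports an exposed pregnancy only above one tablet a day, so pregnancies exposed at the trial dose get no routine safety report and no follow-up to outcome

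*Protocol*

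**What the plan says.** Section 8.4 is the protocol's only rule on reporting pregnancies. A woman who took the trial drug before her pregnancy was known "will only be reported if the daily dose at least once was higher than one tablet during the time span of undetected pregnancy". For those cases, "Reporting will be made within 24 hours by using the SAE-form".

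The dosing sections fix the regimen:
- 5.1.2 describes tablets with the dose "Daily, 81 – 100 mg (depending on country").
- The first footnote to the Clinical Trial Schedule has patients take the drug at home once a day.
- 5.4.2 states "Maximum dose allowed: 100mg ASA daily, orally".
- 5.4.5 states "No changes in IMP dosage are intended or permitted".

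Other sections treat pregnancy as important. It is an exclusion criterion (4.5), and contraception is required of women who could become pregnant (4.4). Section 4.6.1 lists "Existing or intended pregnancy, lactation in patients of the intervention group" among the possible reasons for withdrawal, while control patients who become pregnant stay in the trial. Section 8.1.2 includes among the seriousness criteria "Is a congenital anomaly/ birth defect or". Under 8.2, the observation period for adverse events "ends with the last study visit, 30 days +/-10 days after end of treatment visit (or after withdrawal").

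**The concern.** A pregnancy reporting rule exists so that the sponsor learns which pregnancies were exposed to the drug and how they ended. Here the condition for a report is a dose above the one the trial gives. The women whom the rule should mainly cover, those exposed while taking the drug as directed, appear to fall outside it.

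Undetected exposure is foreseeable. The schedule places pregnancy tests only at screening and baseline, visits are six months apart, and treatment lasts 36 to 120 months. Section 8.4 itself anticipates exposure before a pregnancy is known.

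What is at stake is the safety record. A congenital anomaly is one of the protocol's own seriousness criteria, yet it usually becomes known only at or after birth. If exposed pregnancies are neither reported nor followed, that criterion depends on someone happening to tell the site.

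**Working it through.** The protocol gives no figure to reproduce here. The check compares sections, with two short pieces of arithmetic.

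**1. Can the trigger be met within the protocol dose?**

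Inputs: tablets, 81 to 100 mg per day (5.1.2); once daily (schedule footnote); maximum 100 mg per day (5.4.2); no dose changes (5.4.5). Tablet strength is not stated. I assume that one tablet is the daily dose, which is the natural reading of these sections.

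Daily dose = tablets per day × tablet strength.

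| Tablets per day | Daily dose | Against the 100 mg maximum | Reported under 8.4? |
|---|---|---|---|
| 1 | 81 to 100 mg | at or below | no |
| 2 | 162 to 200 mg | above | yes |

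In whole tablets, no dose both meets the trigger and respects the maximum.

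How far this rests on the assumption: two tablets stay within 100 mg only if each holds at most 100 / 2 = 50 mg. The protocol describes no such tablet. If one were used, and the daily dose took two of them, every compliant patient would meet the trigger. The finding depends on the one-tablet reading.

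**2. Does observation reach the outcome?**

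Under 8.2, observation ends 30 ± 10 days after withdrawal: 30 − 10 = 20 days to 30 + 10 = 40 days.

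Illustration, with gestational figures that are my assumptions: a 40-week term, with the pregnancy detected and the patient withdrawn at 6 to 12 weeks.
- Time left to birth: 40 − 12 = 28 weeks (196 days) to 40 − 6 = 34 weeks (238 days).
- Gap between end of observation and birth: from 196 − 40 = 156 days to 238 − 20 = 218 days.
- Observation would reach a birth at term only if withdrawal came within 40 days of it, that is after about 40 − 40/7 = 34.3 weeks.

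Section 6.4 also allows the follow-up visit to be waived when no SAE is unresolved at the end-of-treatment visit. In an uncomplicated pregnancy, even that contact is not assured.

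**3. Which other routes exist?**

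| Route | What it captures | What it leaves out |
|---|---|---|
| Withdrawal record (4.6.1) | date and primary reason on the CRF | a safety report; the pregnancy outcome |
| SAE reporting (8.1.2, 8.3) | a serious complication or birth defect, at any dose, within 24 hours of becoming known | the exposure itself; any active enquiry about the birth |
| Continued follow-up of AEs and SAEs (6.4, 8.1.6, 8.2) | events already recorded, until clarified or stable | an uncomplicated pregnancy, which the protocol does not define as an AE |

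None of the three provides a routine report of an uncomplicated pregnancy exposed at the trial dose, or its outcome.

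**The case against.** The strongest reply is that the threshold is deliberate. The word only shows intent, and no other section promises that all exposed pregnancies are reported, so no rule is broken. That stands as far as it goes: this is a choice, not a slip. But the protocol gives no reason for it, and it fits poorly with a seriousness criterion that depends on pregnancy outcomes.

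Three stronger conclusions are tempting, and the protocol does not support them.
- **That a congenital anomaly cannot be observed at the trial dose.** Section 8.1.2 applies at any dose, and 8.3 requires a report once an SAE becomes known, with no tablet condition. Section 8.4 does not switch this off.
- **That the sponsor and the DSMB would see no exposed pregnancies.** The withdrawal reason goes on the CRF, drug supply and return are recorded at each visit (5.4.2), and the DSMB may request further variables (1.4).
- **That the final safety statement must be wrong.** The protocol promises no statement on pregnancy outcomes, and it gives no expected number of pregnancies. With contraception required, the number is probably small.

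Two further points have some force. Section 5.4.4 permits limited additional ASA, for example for migraine. If those tablets counted towards the trigger, a compliant patient could meet it; 8.4 does not say whether they count. A separate Safety Manual is also cited in 8.5 and is not shown. It is cited for second assessment and SUSAR reporting, and 8.4 does not refer to it. It might add something on pregnancies, but it should not have to override an explicit restriction in the protocol.

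**Conclusion.** The point holds in a limited form. For an uncomplicated pregnancy exposed to the trial drug as the protocol directs, there is no routine pharmacovigilance report and no described follow-up to outcome. The birth-defect criterion in 8.1.2 would therefore be ascertained by chance rather than by process in the intervention arm.

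Control patients who become pregnant keep their six-monthly visits, so ascertainment may also differ between the arms. The protocol does not allow the size of that difference to be estimated.

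The conclusion rests on one tablet being the daily dose and on additional ASA not counting towards the trigger. The gap of roughly 156 to 218 days between end of observation and birth rests on the assumed gestational timing. It applies to women who are withdrawn, since 4.6.1 lists pregnancy as a possible reason rather than an automatic one.

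The number of women affected is unknown. The primary analysis and sample size are unaffected. This should be fixed, but it does not put the trial's main result in doubt.

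**What to change.** Amend 8.4 to remove the tablet condition. Require a report within 24 hours for every pregnancy with any exposure to the trial drug, whatever the tablet count, and require the pregnancy outcome to be recorded. Add this outcome follow-up to 8.2 as an exception to the end of observation, and align 4.6.1 so that a withdrawal for pregnancy leads to the 8.4 report. This changes reporting only, not dosing or care.

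The cost is amendment wording, a pregnancy form, and probably a few reports. The small downside is that follow-up for these women will run past the last study visit. Last subject out is planned for Q2 2029 (3.2), so under that timeline the change would apply to years of remaining treatment from this 2022 version.

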### 8.5 Expedited Reporting

SUSARs are to be reported to the responsible ethics committees, the competent authorities, if applicable other institutions according to national regulations and to all participating investigators within defined timelines, i.e. they are subject to an expedited reporting.

All SAEs will be subject to a second assessment by a designated person. Procedures and responsibilities regarding second assessment are described in a separate document (Safety manual).

The second assessor will fill out a 'Second Assessment Form' for each SAE and send it back per fax to the responsible person at the KKS Heidelberg within 48 hours, fax-number:

**[name]**

The 'Second Assessment Form' will contain the following information:

- I) Assessment of relationship between SAE and IMP (causality)
- II) Assessment of expectedness of SAE (derived from SmPC)
- III) Assessment of relationship between SAE and the underlying disease
- IV) Statement if the benefit/ risk assessment for the trial did change as a result of SAE.

The expedited reporting (to competent authorities, responsible ethics committees and investigators) will be carried out by a responsible Safety Officer at KKS Heidelberg. Only SUSARs/ SAEs occurring after administration of IMP will undergo expedited reporting. Details concerning the reporting of SUSARs will be described in a separate document "Safety Manual".

## 9 STATISTICAL PROCEDURES

### 9.1 Sample Size Calculation

The test of the primary hypothesis is outlined in paragraph 9.4 (Statistical Methods). The sample size calculation is based on the following assumptions:

Previously a hazard ratio of 1.3 (95%CI 1.0-1.9) for hypertension as a risk factor for aneurysm rupture (PHASES cohort) and an odds ratio of 0.27 (95% CI 0.27-0.67) for risk of rupture in patients with unruptured intracranial aneurysms using ASA was reported. If we conservatively assume a risk reduction of 45% for the primary outcome measure and the risk to have a primary outcome event at three years of 15% in the standard treatment group and 8.25% in the intensive treatment + ASA group, an alpha of 0.05 and a power of 80%, 353 patients are needed in each group. Assuming a dropout rate of 10%, we will need to assign 776 patients to the trial so that 706 patients can be analyzed.

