|                       | 
Exclusion Criteria
 
 
All non-saccular UIAs or aneurysms related to arteriovenous malformations
 
Daily ASA already prescribed for another indication
 
Use of a vitamin K antagonist or direct oral anticoagulant (DOAC) at baseline
 
History of hypersensitivity/allergy to ASA or to any other drug with similar chemical structure or to any excipient present in the pharmaceutical form of ASA
 
History of asthma induced by ASA or other anti-inflammatory drugs
 
Other contra-indications for low-dose ASA (81 mg - 100 mg per day) not yet mentioned, (e.g. bleeding disorders, , gastric ulcers and/or intestinal ulcers, acute liver failure of kidney failure, severe heart failure, treatment with methotrexate in a dosage 15 mg/week or above)
 
Use of another platelet aggregation inhibitor, which in combination with ASA would give an unacceptable risk of side effects/complications
 
Chronic kidney disease stage IV and V (GFR < 30 mL/min/1.73 m^2)
 
Pregnancy and lactation
 
Participation in any other interventional clinical trial
 
Life-expectancy <3 years
 
 |
| SAMPLE SIZE    | 
To be assessed for eligibility: (n = 2500)
 
To undergo screening examination: (n=970)
 
To be assigned to the trial: (n = 776)
 
To be analysed: (n = 705)
 
Assuming a risk reduction of 45% for the primary outcome measure and the risk to have a primary outcome event at three years of 15% in the standard treatment group and 8.25% in the intensive treatment + ASA group, <math>\alpha=0.05</math> and <math>\beta=0.20</math>, 353 patients are needed in each group. Assuming a dropout rate of 10%, we will need to assign 776 patients to the trial so that 705 patients can be analysed.
  |
| TRIAL DURATION | 
Total trial duration: [162 months]
 
Duration of clinical phase: [144 months]
 
Beginning of the preparation phase: [Q2 2017]
 
FSI (first subject in): [Q3 2017]
 
LSI (last subject in): [Q2 2026]
   |

|                             |  |
|-----------------------------|--|
|                             | LSO (last subject out): [Q2 2029]
DBL (database lock): [Q3 2029]
Statistical analyses completed: [Q4 2029]
Trial report completed: [Q2 2030]  |

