CTAs/MRAs beyond this time point will also be uploaded to the central server. We will collect data on GFR and blood sodium in patients with pre-existing, compensated chronic renal failure (stage III: GFR <60 mL/min/1.73 m^2), who are monitored for these parameters by their treating physicians. During all trial visits the investigators will stress that smoking cessation is pivotal and inform patients who smoke about possible options for help in smoking cessation. The number of cigarettes per day and alcohol consumption per day will be recorded. The investigator will collect data on GFR and blood sodium in patients with pre-existing, compensated chronic renal failure (stage III), who are monitored for these parameters by their treating physicians.

Any subsequent imaging during the study period will be uploaded to the core lab. Timing and frequency of subsequent CT- or MR examinations vary in clinical practice. In case the 36 ( $\pm 6$ ) months' time point is not sampled in a particular patient, the latest CTA/MRA prior to this date will be analysed. Patients with imaging using different imaging modalities (e.g. initial MRA vs. subsequent CTA) will be excluded from assessing the images for the primary endpoint and considered to be dropouts in the statistical analysis. However, for patients with several images of the same modality, an analysis for the time span between these two identical modalities may be permitted by the adjudication committee.

At each treatment visit, remaining trial medication will be collected, the number documented and the blisters will be sent back for disposal. New trial medication is provided for the next period.

End of treatment visit will be planned 36 months after inclusion of the last patient. The same procedures are performed as in treatment visits. Patients should be asked to continue study participation/ treatment until month 120 ( $\pm 30$  days) or end of study (whatever comes first).

In case of intolerable AEs/ SAEs, new visits will be planned by the investigator until the findings have been clarified or became stable.

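### Enrolling 776 patients with 10% dropout leaves about 698 to analyse, not the 706 of section 9.1 or the 705 of the synopsis; the cost in power is about 0.4 percentage points

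*Protocol*

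**What the plan says.** Section 9.1 sets out the primary-outcome assumptions: "conservatively assume a risk reduction of 45% for the primary outcome measure", with "the risk to have a primary outcome event at three years of 15% in the standard treatment group and 8.25"% in the intervention group. From these, with "an alpha of 0.05 and a power of 80%, 353 patients are needed in each group". The dropout step follows directly: "Assuming a dropout rate of 10%, we will need to assign 776 patients to the trial so that 706 patients can be analyzed".

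The synopsis, in its sample size row, repeats the same risks and the same 353 per group, but ends differently: "Assuming a dropout rate of 10%, we will need to assign 776 patients to the trial so that 705 patients can be analysed". It also lists 705 separately as the number to be analysed.

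Section 4.1 carries the enrolment figure forward as 776, or 388 per group, and refers back to section 9.1. Section 9.4 uses 776 again to set the ceiling on patients with aneurysms under 3 mm. The formula that turns 353 per group into 776 is not given anywhere in the protocol.

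**The concern.** There are two inconsistencies.

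- The three figures in the section 9.1 sentence (10% dropout, 776 assigned, 706 analysed) cannot all be true. Neither can the synopsis set (10%, 776, 705).
- The two places disagree on the analysed number. The synopsis also disagrees with itself, since 2 × 353 = 706, not 705.

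The power statement is tied to 353 analysable patients per group, which is the smallest whole number that reaches 80% under the stated assumptions. If enrolment and dropout together deliver fewer than that, the stated power is not quite what the stated plan gives. Section 9.4 also asks the DSMB to check the sample size assumptions and lets it recommend a new sample size. For that it needs one coherent set of figures to check against.

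**Working it through.** **Inputs, all from section 9.1 except the allocation (5.5.1) and the enrolment per arm (4.1):** control risk p1 = 0.15; intervention risk p2 = 0.0825, since 0.15 × (1 − 0.45) = 0.0825; alpha 0.05, sidedness not stated; power 80%; 1:1 allocation; dropout 10%; 776 assigned, 388 per arm.

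**Step 1: reproduce 353 per group.** Two-sided pooled formula without continuity correction:

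n = [1.960 × √(2p̄(1 − p̄)) + 0.8416 × √(p1(1 − p1) + p2(1 − p2))]² / (p1 − p2)²

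- p̄ = (0.15 + 0.0825)/2 = 0.11625, so √(2 × 0.11625 × 0.88375) = 0.4533
- √(0.1275 + 0.0757) = 0.4508
- n = (0.8884 + 0.3794)² / 0.0675² = 352.8, rounded up to 353

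This matches the protocol exactly. Other methods do not: unpooled 351, arcsine 347, log risk ratio 369, continuity-corrected 382, one-sided 278. The pooled two-sided formula is therefore used below.

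**Step 2: apply 10% dropout to 776.**

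- 776 × 0.9 = 698.4, about 698; per arm 388 × 0.9 = 349.2, about 349
- Shortfall: 706 − 698 = 8 against section 9.1, and 705 − 698 = 7 against the synopsis, about 1% in either case

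**Step 3: dropout that the printed figures imply.**

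- 1 − 706/776 = 9.0%
- 1 − 705/776 = 9.1%

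**Step 4: enrolment needed for 706 at 10% dropout.**

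- In total: 706/0.9 = 784.4, so 785
- By arm: 353/0.9 = 392.2, so 393, giving 786

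**Step 5: where 776 may come from.**

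- 353 × 1.1 = 388.3, which gives 388 per arm and 776 in total
- 705 × 1.1 = 775.5, which also rounds to 776
- 706 × 1.1 = 776.6, which rounds to 777 and does not match
- Division by 0.9 gives 784 or more from either total

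Multiplying by 1.1, per arm or from 705, fits the printed numbers. This is an inference.

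**Step 6: power, same formula.** Power = Φ[(0.0675 × √n − 0.8884)/0.4508]

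| Analysed per arm | Power |
|---|---|
| 353 | 80.0% |
| 349 | 79.6% |

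**The case against.** The strongest reply is that the slip does not matter. Seven or eight patients are about 1% of the analysed number, and both 79.6% and 80.0% round to the stated 80%. The protocol does not name its formula; at 349 per arm the unpooled version gives 79.9% and the arcsine version 80.2%. This stands as a judgement of size, and it is why no extra enrolment is proposed. It does not make the sentence correct, and the pooled formula is the one that reproduces 353.

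A second reply is that dropouts may not be lost. Section 4.6.1 carries the last imaging forward for early withdrawals, and section 9.2 defines the primary set as all randomised patients. Some dropouts may therefore contribute, and the number analysed may exceed 698. That also stands, but section 9.1 itself treats dropouts as unavailable, and its figures must agree on that footing.

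A reader might go further and infer that no allowance was made for patients who switch imaging modality, and that they push power well below 80%. The protocol does not support this. Section 6.3 says such patients are "considered to be dropouts in the statistical analysis", so they may already sit within the 10%. It gives no rate for switches, and it lets the adjudication committee permit an analysis where a same-modality pair of images exists. Any power figure for this loss would rest on an invented rate.

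**Conclusion.** The error is certain and its effect is minor. With 776 assigned and 10% dropout, about 698 patients remain (349 per arm), not 706 or 705. Power is 79.6% rather than 80.0%, a loss of about 0.4 percentage points. That figure assumes the stated risks of 15% and 8.25%, a two-sided alpha of 0.05, the pooled two-proportion formula, and dropouts that contribute nothing to the analysis.

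The calculation of 353 per group is sound; only the step from there to 776 fails. It would be too strong to state as fact that the sample was multiplied by 1.1, because the protocol does not show the step. It would also be too strong to call the trial materially underpowered on this account. The difference between 705 and 706 needs no calculation and should be settled at the same time.

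**What to change.** Correct the text in the synopsis and in section 9.1 without enrolling more patients. Choose one of two statements:

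- 776 patients allow for 9% dropout, leaving 706 to analyse (776 × 0.91 = 706.2); or
- 776 patients with 10% dropout leave 698 to analyse, with 79.6% power under the stated assumptions.

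Use the same analysed number in both places, including the separate line in the synopsis that now reads 705. The enrolment figures in section 4.1 and the ceiling in section 9.4 rest on 776, which does not change, so they can stay.

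The cost is a wording change. Under the first option the dropout allowance becomes slightly tighter; under the second the stated power becomes slightly less favourable. Neither affects recruitment, conduct or the analysis.
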